subjects without a known diagnosis. This will be performed by a trained technician and read by an experienced radiologist. This is not formally used for study eligibility but may be used to inform subjects that they do not seem to have fatty liver and may not want to undergo the remainder of screening procedures.

Whole Body DXA, Assessment of Nutrition and Activity: CRC bionutrition staff will perform the following assessments: Whole body DXA will be used to determine whole body and regional fat. The technique has a precision error (1 SD) of 3% for fat and 1.5% for lean body mass (97). 24-hour food recall will be administered to assess micronutrient and macronutrient intake, and Modifiable Activity Questionnaire (MAQ) will be administered to assess physical activity (98).

Medication adherence will be assessed by vial count and medication diary.

V. Biostatistical Analysis

Endpoints

Aim 1: Change in hepatic fat fraction as measured by ¹H-MRS after 1 year of randomized treatment (**Primary endpoint, Aim 1a**). Histological features of NASH, assessed by histopathological analysis of liver biopsy, including frequency of ≥ 2 point reduction in NAFLD activity score (NAS score) with no worsening of fibrosis stage and reduction in individual components of the NAS (**Aim 1b**).

Aim 2: Change in post-prandial hepatic DNL by stable isotope methods (**Aim 2a**). Change in mRNA expression of genes related to hepatic lipid metabolism in liver tissue obtained by biopsy. Target genes will include SCD1, FAS, SREBP1c, CD36, PPAR α , PPAR γ , CPT1, LDLR (**Aim 2b**). Change in mRNA expression of genes related to inflammation/oxidative stress and fibrosis/fibrogenesis in liver tissue. Target genes include: MCP1, TNF α , IL-1 β , IL-6, IL-18, TLR, MyD88, CCL5, TGF β 1, NF κ B, TIMP1, COL1A1, MMP 1-14 (**Aim 2c**). Exploratory endpoint: change in immune cell phenotypes assessed by flow cytometry

Aim 3: Change in circulating fasting lipids, c-reactive protein, tissue plasminogen activator antigen, plasminogen activator inhibitor-1 antigen, adiponectin, and potentially other circulating markers as guided by emerging science regarding noninvasive CVD risk measures (**Aim 3a**).

Supportive endpoints of interest include change in liver stiffness measured by fibroscan, change in AST, ALT, and GGT, and change in fasting glucose, insulin, and HOMA-IR.

Planned Data Analysis

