intake are contributing to the observed treatment effect on hepatic fat, histologic and metabolic variables. If so, we will include these variables in the analyses and modeling as adjusted covariates. If any other variables are different between groups, such as medication adherence, these will also be included as covariates.

Genetic analyses: Hepatic mRNA expression for the targeted genes listed above will be quantified at baseline and 12 months. Our statistician, [name], has designed a stepwise analysis that will serve as an appropriate approach for this sample size and the discrete set of genes that we propose to measure. (1) We will first assess whether there are significant changes in expression between baseline and 12 months in the GHRH-treated subjects, using paired samples t-test. (2) For genes that show a significant change in expression in this analysis, we will then compare fold-changes in expression between the tesamorelin and placebo groups. False discovery rate based type-1 error adjustment will be applied for multiple comparisons. (3) Genes with differential changes in the tesamorelin vs. placebo groups will be further investigated by assessing associations between mRNA expression and histological and biochemical parameters. For example, if SREBP1c is found to be downregulated in tesamorelin compared to placebo groups, we will assess correlations between mRNA expression of SREBP1c and histological steatosis score as well as rate of *de novo* lipogenesis quantified using stable isotopes.

Missing data: We expect that the pattern of any missing data will be at random (MAR), and the longitudinal mixed effects model approach utilizing all available observation will provide unbiased effect size estimates. However, we will perform sensitivity analyses if the dropout rate is higher than expected or differs between groups. We will initially consider applying the last observation carried forward (LOCF) as a conservative approach. We will also consider multiple imputations (MI) based analysis.

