Aim 1a (Primary endpoint): In our previous study of tesamorelin in HIV (see Preliminary Data), the change in liver fat over 6 months among individuals who started with hepatic fat fraction >5% was -2.5 ± 11.9 lipid-to-water percent in placebo vs. -9.1 ± 7.6 lipid-to-water percent in tesamorelin. Based on the prior data, we assumed that the pooled standard deviation of the 1 year change is 8% and the tesamorelin treatment effect over 1 year (difference in tesamorelin vs. placebo changes) is at least a 7 point change in the lipid to water percentage. Using this data we estimate that an initial sample size of 76 will provide 91% power to detect a clinically relevant treatment difference of 7% or larger 1 year mean changes in liver fat (lipid to water %) at $\alpha = 0.05$ if the discontinuation rate is 20% (61 evaluable patients), or 80% power if the discontinuation rate is 25%. In the prior study of tesamorelin led by [name], discontinuation rate was 14% after 6 months (69). These assumptions are conservative as we expect that the 1 year mean change in the current proposed trial among the patients on tesamorelin will be greater than that was observed above in our 6 month preliminary studies. We also anticipate the variability over time will be less in the placebo group assessed by repeated measures in the proposed study rather than a single point in time as in our prior study. **Aim 1b:** Based on baseline data from PIVENS (25), in which the standard deviation in NAS is 1.4, we will have >90% power to detect a change of 2 in NAS. **Aims 2-3:** For analysis of the variables in Aims 2-3, it is important to note that the purpose of the study is to interrogate physiology, and the sample size is relatively limited due to the detailed assessments performed. Thus, these variables will be largely viewed as hypothesis generating, and statistical analyses will be interpreted in such a context. (For example, if there is a marginally significant change in one lipogenic gene but no signal in other genes, this will not be considered meaningful, whereas a trend toward change in all

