lipogenic genes in the same direction may be meaningful). Thus we do not plan to correct Type 1 error for multiple comparisons, which would limit power and increase the probability of Type 2 error (99, 100). For the variables in Aims 2-3, the sample size will provide 80% power to determine a 0.73 SD difference in 1 year mean changes between treatment groups at $\alpha = 0.05$ with 61 evaluable patients. Although changes of <0.7 SD in some of these variables may be clinically relevant, most clinically meaningful effects are expected to be 1SD or more, a magnitude for which the study is sufficiently powered.

VI. Risks and Discomforts

GHRH (Tesamorelin)

In previous large, placebo-controlled studies of tesamorelin in HIV-infected individuals, adverse events that were more common in the treatment vs. placebo group were injection site erythema (8.5% in treated vs. 2.7% in placebo), injection site pruritis (7.6% of treated vs. 0.8% placebo), and peripheral edema (6.1% in treated vs. 2.3% in placebo). With respect to serious adverse events (SAEs), prevalence was not statistically different (3.7% in treated vs. 4.2% in placebo). There is a risk of hyperglycemia with GHRH, particularly in the few weeks following initiation of treatment, but glycemia returns to baseline after several months. Clinically significant changes have not been observed for liver function (alanine aminotransferase or aspartate aminotransferase), kidney function (creatinine), or blood pressure (diastolic and systolic).

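### Genes are screened on the tesamorelin arm's own change before the arms are compared, so the promised false discovery control is not assured, placebo-only change is missed, and another section rules out any correction

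*Combined protocol and SAP*

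**What the plan says.** Section V, Planned Data Analysis, Genetic analyses, sets out three steps.

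1. Screening within one arm: "We will first assess whether there are significant changes in expression between baseline and 12 months in the GHRH-treated subjects". A paired t-test is named for this.
2. Comparison of tesamorelin with placebo, for survivors of the screen only: "For genes that show a significant change in expression in this analysis, we will then compare fold-changes in expression". On multiplicity the paragraph adds: "False discovery rate based type-1 error adjustment will be applied for multiple comparisons".
3. Genes that differ between arms go forward to correlations with histological and biochemical measures, such as steatosis score and de novo lipogenesis.

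The screening alpha is not stated. Nor are the FDR method, its level, the step it applies to, or whether the family is all genes or only survivors.

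Section V, Endpoints, places hepatic mRNA expression in Aims 2b and 2c. For Aim 2b, "Target genes will include SCD1, FAS, SREBP1c, CD36" and four more; Aim 2c lists inflammation and fibrosis genes.

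Section V, Sample Size and Power Calculations, covers Aims 2-3 together: "these variables will be largely viewed as hypothesis generating". It uses genes as its example: "if there is a marginally significant change in one lipogenic gene but no signal in other genes, this will not be considered meaningful". It then concludes: "Thus we do not plan to correct Type 1 error for multiple comparisons".

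**The concern.** There are three separate problems.

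- **The screen and the test share data.** A gene with no treatment effect passes step 1 when the tesamorelin mean is by chance far from zero. The same chance deviation then pushes the between-arm difference away from zero in step 2. The p-values of survivors are no longer uniform under the null, so an FDR procedure applied to them need not keep its level.
- **The screen looks at one arm only.** If expression worsens on placebo and tesamorelin prevents this, the treatment effect is real, but the tesamorelin arm shows no change and the gene is dropped before the arms are compared.
- **The multiplicity rules conflict.** One paragraph promises FDR adjustment for the genes. Another says the aims that contain them get no correction.

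At stake is the list of genes reported as changed by treatment, and the step 3 correlations built on it.

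**Working it through.** **Inputs from the plan.** Allocation is 1:1, with 61 evaluable patients (76 x 0.80 = 60.8) and alpha 0.05. The gene list has 8 lipid genes, 10 inflammatory genes (TLR counted once), TIMP1, COL1A1 and up to 14 MMPs: 8 + 10 + 2 + 14 = 34, or 20 without the MMPs.

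**Assumptions, because the plan is silent.** Two-sided screen at 0.05; Benjamini-Hochberg (BH) at q = 0.05 over survivors; normal change scores with SD 1 in both arms; correlation between genes 0, 0.3 or 0.5. Between-arm tests are not adjusted for baseline.

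**The plan's own figure reproduces.** For a two-sample t-test with 30 and 31 patients, the noncentrality is 0.73 / sqrt(1/30 + 1/31) = 0.73 / 0.256 = 2.85. On 59 degrees of freedom this gives 80.1% power, as stated for 0.73 SD.

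**Dependence of the two tests.** With known variance and no effect, the correlation between the screening statistic and the between-arm statistic is sqrt[(1/nT) / (1/nT + 1/nP)] = sqrt[nP / (nT + nP)] = sqrt(31/61) = 0.71. In simulation, a null gene that passes the screen has a 33-35% chance of between-arm p < 0.05 (34 genes, none responding) instead of 5%. About 34 x 0.05 = 1.7 null genes pass per trial. BH over one or two survivors therefore adjusts very little.

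**Simulated FDR** (4,000 runs per scenario, 31 vs 30 patients, 34 genes):

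| Truth | BH over survivors, correlation 0 / 0.3 / 0.5 |
|---|---|
| No gene responds | 30 / 25 / 17% |
| 2 genes, 0.73 SD | 15 / 13 / 10% |
| 5 genes, 0.73 SD | 7.4 / 6.7 / 6.5% |
| 10 genes, 0.73 SD | about 4% |
| Both arms shift 0.3 SD, no gene responds | 6.8 / 4.8 / 3.5% |

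BH over all 34 between-arm p-values gives 3-5% throughout. A separate run with 30 tesamorelin and 31 placebo patients gave 33 / 26 / 18% with no response, and 24 / 17 / 15% with 20 genes. With 20-25 biopsied patients per arm (correlation 0.3), the no-response figure is 26-27%.

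**Placebo-only change.** A gene that is flat on tesamorelin passes a 0.05 screen 5% of the time, so its power cannot exceed 5% whatever happens on placebo. For a 0.8 SD placebo rise, simulated per-gene power is 3% with the screen. Without it, power is 43-45% (one such gene) or 56-59% (five). At 0.73 SD with independent genes the comparison is 2.9% against 40% (three genes) to 53% (eight).

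**Keeping the screen but using 34 as the BH denominator.** FDR is 1.7-4.1%. This rule finds 2.2-2.3 of 5 true genes, the same as dropping the screen, and placebo-only power stays at 2-3%.

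**The case against.** The strongest reply is that the high figures depend on one reading. The FDR sentence follows both tests and is not limited to step 2. If BH at 5% is applied at the screen as well, simulated FDR is about 2-4% with 0 to 10 responding genes and no shared drift. That rule also keeps most of the yield: about 1.3 of 2, 3.6 of 5 and 7.4 of 10 true genes. This stands as far as it goes: the FDR result depends on a detail the plan omits. But when both arms drift by 0.2-0.3 SD and no gene responds, the two-step rule gives 8-18%. It also finds placebo-only change less than 1% of the time.

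Second, the plan treats these endpoints as largely exploratory and discounts an isolated marginal gene. This is real mitigation. In no-response runs with a false discovery, 61-77% had exactly one, and two or more false genes arose in only 7-10% of no-response trials. But the rule is informal, its example is confined to lipogenic genes, and it does not replace the FDR control the plan promises.

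Third, Aims 2b-2c predict change on tesamorelin, so screening on it may seem to match the hypothesis. Yet the effect of treatment in a randomized trial is the difference between arms, and the screen discards one way of producing it. The size of that loss depends on the assumed effect: at 0.73 SD and correlation 0.3, unscreened power is 33% (one gene) or 45% (five).

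Fourth, the Genetic analyses paragraph could be an exception to the general no-correction statement. The plan does not say so, and that statement uses genes as its own illustration.

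**Conclusion.** The concern holds. The contradiction between the two sections, and the near-total loss of placebo-only change, do not depend on how the FDR sentence is read. FDR control is not assured. Under an unadjusted 0.05 screen with BH over survivors, which is the natural reading but not a stated one, FDR is 17-30% if no gene responds and 10-15% with two responders. It is 6.5-7.4% with five and near nominal with ten, or when both arms shift substantially together. These sizes rest on the assumed gene count, screening alpha, q, correlation and normal changes of equal SD. The endpoints are secondary and largely hypothesis generating, and the primary liver-fat conclusion is unaffected. The plan should be corrected before the gene data are analysed.

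**What to change.** - Remove the tesamorelin-arm test as a gate and report within-arm changes descriptively.
- Compare arms for every prespecified gene in Aims 2b-2c, adjusting for baseline expression. The simulations used unadjusted changes, so the error control shown does not rely on that adjustment.
- Fix the gene list from the Endpoints section. Specific Aim 2b names only 5 of its 8 lipid genes, and TLR needs a named gene.
- Apply Benjamini-Hochberg at a stated q over the full list.
- Amend the Sample Size section so that FDR applies to the gene set, while the other Aims 2-3 variables stay uncorrected and hypothesis generating.

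This needs wording only and no new data, but it costs nominal discoveries. With 0.73 SD effects, the number of true genes found falls from about 1.5 to 0.7 of 2, from 3.6-3.7 to 2.2-2.3 of 5, and from 7.2-7.6 to 5.3-5.6 of 10. With few responders, part of the larger yield came without assured error control. With about ten, the screened rule stayed near 4% FDR, so there the loss is real.

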Subjects who have symptoms that may be consistent with growth hormone excess, including myalgia, arthralgia, paresthesia, or edema, will be offered a dose decrease to 1mg daily or the option to discontinue the study. Subjects who opt for a dose reduction and still have these symptoms will be discontinued from the study if the investigator judges the symptoms to be greater than mild in nature.

With regard to injection site reactions, subjects will be informed to notify a study investigator of any sign of erythema, swelling, or pruritis. Subjects who notify us of such reactions will be asked to stop the study drug and come in for a supervised injection with a study investigator. If the reaction is not present during the supervised injection, and the subject feels comfortable continuing, s/he may restart drug with careful instructions to call again if they experience any erythema, swelling, or pruritis. Subjects with reports of these symptoms on two separate occasions, or any subjects with erythema and/or pruritis extending beyond the immediate injection site will be discontinued from the study. Subjects will be informed to seek emergency medical care immediately if they are experiencing any signs of allergic reaction such as hives, generalized urticaria, nausea, abdominal pain, vomiting, dizziness, syncope, difficulty breathing, incontinence, or general feeling of unwellness. Any subject who has any one of these symptoms in temporal combination with urticaria, redness, or swelling at the injection site will also be discontinued from the study.

Subjects with fasting glucose of > 126 mg/dL or HbA1c $> 6.5\%$ at any visit, confirmed by a re-draw, will be discontinued from the study. Although there are not plans to check random glucose levels, if any subject

has a random glucose level checked for other reasons that is ≥ 200 mg/dL, we will perform a fasting glucose. If this fasting glucose is ≥ 126 mg/dL, verified on repeat, this subject will be discontinued from the study.

Any subject with an evolving medical condition (e.g., progressive liver disease) such that continued participation in the study may incur risk or preclude appropriate clinical management will also be discontinued. Subjects with cirrhosis or decompensation during the trial will be discontinued. A physician or NP will be available 24/7 to subjects for any questions or concerns about the study drug.

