Abnormal liver function tests will be managed per the algorithm below. If AST or ALT are ≥ 8 x ULN or 600 IU/L, we will ask patients to return within 1 week for CPK and LDH as needed for the algorithm.

Monitoring and Algorithm for Drug Induced Liver Injury

A. If isolated transaminase (AST or ALT) elevations are observed, defined as:

Normal bilirubin and absence of clinical hepatitis, AND

- ALT or AST ≥ 5 times the ULN if normal at baseline, OR
- ALT or AST ≥ 3 times the baseline or 400 U/L if abnormal at baseline

THEN

- Repeat liver profile (ALT, AST, bilirubin and PT/INR) within 2 to 3 days and
- Monitor the patient with laboratory testing and physical examination 2 to 3 times per week as per the “close observation” definition in the DILI guidance (<https://www.fda.gov/downloads/Drugs/.../Guidances/UCM174090.pdf>).
- We will be in close communication with the patient’s hepatologist and, if the abnormalities are thought to be related to study drug or do not have another reasonable explanation, we will permanently discontinue study drug

B. If any ONE of the following criteria is met:

- Transaminases (ALT or AST ≥ 3 x baseline) AND bilirubin (total bilirubin > 2 x ULN);
- Cholestatic markers (ALP or GGT > 2 x baseline);
- Isolated ALT/AST ≥ 8 x ULN or 600 U/L in presence of normal CPK and LDH and not secondary to cholangitis
- INR increase > 1.5
- OR: if any ONE of the following criteria is met for total bilirubin unrelated to hemolysis:
 - Doubling of total bilirubin
 - OR: any increase in total bilirubin if: there are symptoms of clinical hepatitis (e.g., vomiting, nausea, right upper quadrant pain)
 - OR: there are immunological reaction (rash or $> 5\%$ eosinophilia),

THEN

1. study medication will be permanently discontinued
2. a drug-induced liver injury workup must be initiated for alternate etiologies;
3. repeat liver profile (ALT, AST, total bilirubin, direct bilirubin, ALP) and PT/INR within 48 to 72 hours;
4. monitor the subject with further laboratory testing and physical examination 2 to 3 times per week as per the “close observation” definition in the DILI guidance (<https://www.fda.gov/downloads/Drugs/.../Guidances/UCM174090.pdf>).
5. If a subject lives in a remote area, they can be tested locally and the results communicated to the investigator promptly.

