6. Subjects will be followed by the study investigator until changes are resolved or stabilized but will not come for further study visits apart from those related to safety monitoring of liver injury.

Individual stopping rules

Subjects will be discontinued from the study for any of the following:

- Fasting glucose > 126 mg/dL confirmed on a re-draw
- HbA1c $> 6.5\%$ confirmed on a re-draw if participant wishes
- IGF-1 Z-score persistently ≥ 3 after dose reduction
- Erythema or pruritis extending beyond the immediate injection site, indicating allergic reaction
- Pregnancy

- Development/diagnosis of active malignancy
- Significant symptoms of GH excess felt to be related to the study drug
- Clinical conditions, which in the best judgment of the investigator are believed to be harmful or potentially life-threatening to the participant, even if not felt to be related to the study drug and/or not addressed in the AE management section of the protocol.
- Request by participant to terminate study product(s)/intervention(s)

Because some of the follow-up study procedures, including liver biopsy and cardiac CT scan, have associated risks, there are no plans to continue following subjects who have discontinued study drug unless otherwise specified above, apart from the possibility of conducting an early termination visit as described above and/or ensuring return to baseline health for subjects who have had an adverse event.

Concomitant Medications

Concomitant medications will be documented at the screening visit and any change in medications will be carefully documented at each subsequent visit. All concomitant medications are allowed unless specifically prohibited in the eligibility criteria above. Given the possibility for growth hormone to affect CYP450, we have excluded patients receiving anticonvulsants or cyclosporine, as well as subjects who require corticosteroids for adrenal insufficiency. (Systemic corticosteroid use within 6 months of the study is also an exclusion criterion.) Subjects who are taking sex steroids or using other forms (e.g., topical) of corticosteroids will be warned that there may be an effect of the study drug to reduce the systemic concentration of these medications, and that we will speak with their prescribing physicians about this if requested.

Study stopping/pausing rules

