Open label analysis: For the 6-month open-label extension, hepatic fat and relevant secondary endpoints including fibrosis as assessed by Fibroscan, and AST and ALT will be determined. We will first examine the 18 month effects by comparing 0-18 months mean change of Group 1 (initially randomized to tesamorelin and maintaining active treatment from month 12-18) to that of Group 2 (initially randomized to placebo and crossed over to tesamorelin from months 12-18) using independent samples t-test, and then compare mean change over 1 year to that over the later 6 months within Group 1 using paired samples t-test. Although the primary purpose of the 6-month open label extension is to increase recruitment and retention, analysis of data from the group receiving tesamorelin for 18 months will provide information regarding whether reductions in liver fat translate into sustained longer-term improvements in transaminases and liver fibrosis as measured by FibroScan and will provide longer-term safety data in this group.

Sample Size and Power Calculations

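### The 18-month AST/ALT and FibroScan t-tests can use only patients with a month-18 value, yet patients stopped under the liver rules are not followed to month 18

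*Combined protocol and SAP*

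**What the plan says.** **Analysis (Section V, Open label analysis).** Hepatic fat, FibroScan, AST and ALT are the outcomes of the extension. The first test is an independent-samples t-test "comparing 0-18 months mean change of Group 1 (initially randomized to tesamorelin and maintaining active treatment from month 12-18") with that of Group 2, who switch from placebo to tesamorelin at month 12. The second is to "compare mean change over 1 year to that over the later 6 months within Group 1 using paired samples t-test". The stated value of the extension lies in "analysis of data from the group receiving tesamorelin for 18 months", which is to show whether there are "sustained longer-term improvements in transaminases and liver fibrosis as measured by FibroScan and will provide longer-term safety data in this group".

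**Stopping (Section IV).** In the drug-induced liver injury algorithm, any one Part B criterion means that "study medication will be permanently discontinued". Part A covers isolated AST/ALT rises and leads to a permanent stop only if the rise is attributed to study drug or has no other reasonable explanation. Under Study Drug, "Subjects with cirrhosis or decompensation during the trial will be discontinued". An evolving condition such as progressive liver disease leads to discontinuation where staying in the study may carry risk or hinder proper care.

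**Follow-up after a stop (Section IV).** Patients stopped under Part B are followed until the changes resolve or stabilise but "will not come for further study visits apart from those related to safety monitoring of liver injury". More generally, "there are no plans to continue following subjects who have discontinued study drug unless otherwise specified above", apart from a possible early termination visit and follow-up of adverse events. The early termination visit is at the discretion of the Co-PIs.

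**General provisions (Section V, Planned Data Analysis and Missing data).** Analysis is by intention to treat with all available data, including data from non-completers. A mixed model is specified for outcomes measured at 0, 6 and 12 months and extended to other repeated measures. LOCF or multiple imputation is considered if dropout is higher than expected or differs between groups.

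**The concern.** AST and ALT are both outcomes of the 18-month analysis and triggers for leaving it. A patient whose values rise far enough can be stopped, has no month-18 value, and drops out of both t-tests; a patient whose values fall stays in. Group 1 is also described partly by what happens after randomisation, namely staying on active treatment from month 12 to 18. No text says how the value that led to a stop, or an early-termination value, enters these tests.

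At stake is the question that the extension is meant to inform: whether improvement is sustained on longer treatment. A mean taken in those who remained on drug can look better than the mean for everyone assigned to it. Section V mentions safety data only in connection with the group treated for 18 months, so the planned safety summary could be read as limited to those patients.

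**Working it through.** **1. Plan figures.** The documents give no sample size, power, attrition or liver-stop figure for the 18-month analysis, so there is none to reproduce. The nearest is for month 12: 76 x 0.80 = 60.8, or 61 evaluable. With a difference of 7 and SD 8 this gives 91.9% power by a t calculation, against the stated 91%. If all-cause discontinuation of 20-25% per year continued at a constant rate (an assumption), the number of Group 1 patients left at month 18 would be 38 x 0.80^1.5 = 27.2 or 38 x 0.75^1.5 = 24.7, about 25-27 of 38. The share stopped for liver reasons is not given.

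**2. Who can enter each test.**

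| Planned test | Values needed | Patient stopped at month 9 | Patient stopped at month 15 |
|---|---|---|---|
| Group 1 v Group 2, 0-18 month change | Baseline, month 18 | Out | Out |
| Group 1, 0-12 v 12-18 month change | Baseline, months 12 and 18 | Out | Out |

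Appendix 1 schedules a liver panel at every visit, so AST/ALT values up to the stop exist, but the t-tests cannot use them.

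**3. Direction and size within Group 1 (illustration).** Let change be normal with SD 1, higher being worse, and remove the worst fraction q. The mean of those left shifts by -phi(z)/(1 - q), where z is the (1 - q) normal quantile. The values of q are assumed.

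| q | Patients of 38 | Shift (SD) | Shift if removal correlates 0.5 with the month-18 value |
|---|---|---|---|
| 2% | 0.8 | -0.05 | -0.02 |
| 5% | 1.9 | -0.11 | -0.05 |
| 10% | 3.8 | -0.20 | -0.10 |
| 15% | 5.7 | -0.27 | -0.14 |

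Example: q = 5%, z = 1.645, phi(z) = 0.103, and 0.103/0.95 = 0.11.

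**4. Group 1 versus Group 2 (illustration).** Apply one common threshold c to both groups. The mean of a group with true mean mu after truncation is mu - phi(c - mu)/Phi(c - mu). Set c so that 5% or 10% of Group 2 (mu = 0) is removed.

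| True Group 1 minus Group 2 | Removed in Group 1 | Bias in the difference |
|---|---|---|
| 0 | 5% or 10% | 0 |
| 0.73 SD better | 0.9% or 2.2% | 0.09 or 0.14 SD against tesamorelin |
| 0.5 SD worse | 12.6% or 21.7% | 0.13 or 0.18 SD for tesamorelin |

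The 0.73 SD is the plan's own detectable difference for Aims 2-3. Example from the last row: c = 1.645, c - mu = 1.145, 0.207/0.874 = 0.237, so the Group 1 mean is 0.5 - 0.237 = 0.263. The Group 2 mean is -0.109. The observed difference is 0.372 against a true 0.5.

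**5. FibroScan.** No stopping rule in Section IV is set on liver stiffness. Selection acts only through the liver-test criteria or a diagnosis such as cirrhosis, so the table in step 3 does not carry over directly.

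**The case against.** The case against has real force. A reader might infer four stronger points that the documents do not support.

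- **That anyone whose liver worsens is removed.** Only threshold-level or clinically risky worsening leads to a stop. Part A is conditional on attribution, and smaller AST/ALT rises and stiffness increases stay in the data.
- **That the result is favourable by construction.** The same liver rules apply to both groups, so the between-group bias can be zero or go either way. Even within Group 1 the tilt is in the mean changes; the paired contrast of the two periods depends on when stops occur.
- **That the plan asserts sustained improvement.** The Open label analysis poses this as a question.
- **That harm is hidden from safety review.** Adverse events and liver injury are followed after a stop, and Section XI has the DSMB review all adverse events.

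Nor can a threshold rise be turned into a bias in U/L: Part A is not an automatic stop, a peak followed until it resolves is not the missing month-18 value, and the number of stops is not given. Section VI also reports no clinically significant AST/ALT changes in earlier tesamorelin studies in HIV, so stops may be few.

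The general provisions do not close the gap. Planned Data Analysis hands the extension over to the later text, which prescribes t-tests. The all-available-data principle cannot put a patient without month 18 into them. The LOCF and imputation analyses are conditional, and expected dropout is stated only for one year. DSMB review is oversight and does not define the safety analysis set.

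**Conclusion.** The concern holds in a limited form. As written, the 18-month AST/ALT and FibroScan tests are completer analyses, and no rule says how stopped patients enter them. For AST/ALT, missingness depends partly on the outcome, and the Group 1 mean change is tilted in a favourable direction. The Group 1 versus Group 2 comparison has no predictable direction of bias: it understates harm if tesamorelin truly worsens the outcome, understates benefit if it truly helps, and is unbiased if the groups do not differ. These statements assume one common threshold; Group 2 in fact spends 12 months on placebo and 6 on drug.

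The size is unknown. The SD figures above rest on assumed removal rates, normality and removal of the worst values, and are illustrations only. The FibroScan effect is indirect and was not quantified. This is a secondary analysis of an extension whose main stated purpose is recruitment and retention; the 12-month primary analysis is not affected. The change is still worth making because a better method is already in the plan.

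**What to change.** In Section V, Open label analysis:

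1. Define Group 1 and Group 2 as all patients randomised to tesamorelin and to placebo.
2. Replace the t-tests with the plan's mixed model on all values from baseline to month 18, with visit as a category so that Group 2's switch at month 12 is allowed for. Include the last scheduled value that led to a stop and any early-termination value. Estimate the 0-18, 0-12 and 12-18 month changes from that model. The t-tests may stay as a labelled completer analysis.
3. Report stops by arm and reason from randomisation. The model relies on data missing at random and does not itself count stops as outcomes, so this table is needed beside it.
4. Summarise longer-term safety for everyone who received tesamorelin, in either phase, not only those who reached 18 months on it.

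**Cost.** SAP wording, one more model and one more table. AST/ALT values are already scheduled at every visit. Little is gained for FibroScan, which is scheduled only at baseline, 6, 12 and 18 months and at the optional early termination visit. The result may look less favourable than the completer figure. No dose, stopping rule or clinical procedure changes.
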